Appendix J: MR-Sequences

Localizer / Scout

2D FLAIR

Turbo Spin Echo (TSE) / Fast Spin Echo (FSE) sequence

TE: 90-140ms

TR: 6000-10000 ms

TI: 2000-2500 ms (use TI according to optimized protocol for specific inversion pulses and field strength)

SENSE / SMASH / GRAPPA / ASSET allowed

Slice orientation: transverse

Slice thickness: 5 mm

Slice gap: 0

Number of slices: same **as sequence 2 (DWI)**

Slice positioning as in **sequence 2 (DWI)**

FOV: 240 mm x 240 mm

Matrix: 256 x 256 or higher

DWI

Single shot EPI sequence

Minimum TE

TR > 3000 ms

Spectral fat suppression

b: 0 and 1000 s/mm² (3 directions)

SENSE / SMASH / GRAPPA / ASSET: optional for 1.5 T, obligatory for 3 T.

Slice orientation: transverse

Slice thickness: 5 mm

Slice gap: 0

Number of slices: Full brain coverage

FOV: 240 mm x 240 mm

Matrix: 128 x 128 or higher

Post-processing: Calculation of ADC maps (diffusion trace maps)

3D T1w pre-contrast (MPRAGE, 3D IR FSPGR T1w)

minimum TE

TI, TR and flip angle according to manufacturer recommendations for optimum image quality

SENSE / SMASH / GRAPPA / ASSET allowed

Slice/3D slab orientation: sagittal or transverse

FOV: 256 mm x 256 mm

Matrix: 256x256

Slice thickness: \leq 1.5 mm

Full brain coverage

Contrast agent injection

0.1 mmol/kg BW of a Gd-based contrast agent

T2w-TSE

Turbo Spin Echo (TSE) / Fast Spin Echo (FSE) sequence

TE: 80-120ms

TR: $^{14}_{12}$ 2500 ms

SENSE / SMASH / GRAPPA / ASSET allowed

Slice orientation: transverse

Slice thickness: 5mm

Slice gap: 0

Number of slices: same as sequence 2 (DWI)

Slice positioning as in sequence 2 (DWI)

FOV: 240 mm x 240 mm

Matrix: 256 x 256 or higher

3D T1w post-contrast (MPRAGE, 3D IR FSPGR T1w)

Sequence parameters and slice positioning as in sequence 1 (3D T1w pre-contrast)

Appendix K: Highly effective birth control methods

Women of childbearing potential (WOCBP) are defined as premenopausal females capable of becoming pregnant (i.e. females who have had evidence of menses in the past 12 months, with the exception of those who had prior hysterectomy).

A highly effective method of birth control is defined as a method which results in a low failure rate (i.e. less than 1% per year) when used consistently and correctly. Such methods include:

- Combined (estrogen and progestogen containing) hormonal contraception associated with inhibition of ovulation (oral, intravaginal, transdermal)
- Progestogen-only hormonal contraception associated with inhibition of ovulation (oral, injectable, implantable)
- Intrauterine device (IUD)
- Intrauterine hormone-releasing system (IUS)
- Bilateral tubal occlusion
- Vasectomized partner
- Sexual abstinence (the reliability of sexual abstinence needs to be evaluated in relation to the duration of the clinical trial and the preferred and usual lifestyle of the patient)

Appendix L: Specific protocol instructions during COVID-19 pandemic

Note: All instructions listed in this Appendix will be solely applicable during the COVID-19 crisis. Furthermore, please ensure that any protocol deviations resulting from COVID-19 are:

Adequately documented in the eCRF's as well as the patient's medical records or in a NTF to be stored in your Study binder (ISF).

Always begin deviation text with "COVID-19"

Introduction

Current information suggests that cancer patients have a higher risk of infection and serious complications from infections including COVID-19, than other patients.

It is strongly recommended that investigators exercise medical/clinical judgement, and decisions regarding each patient should be individualized after considering the overall goals of treatment, the patient's current oncologic status and treatment tolerance as well as their general medical condition.

In addition, investigators should adhere to local and institutional guidelines for SARS-CoV-2 infection and suspected COVID-19 infection

Risk-benefit assessment:

Introduction to trial

The 1608 trial will evaluate a new drug TG02 combined with either radiotherapy or temozolomide, based on the MGMT status in frail, elderly patients (> 65 years old) with newly diagnosed glioblastoma WHO grade 4 and anaplastic astrocytoma. The drugs will also be evaluated as treatment for glioblastoma and anaplastic astrocytoma after first relapse. Assessment of safety and efficacy are objectives of the trial.

Benefits

Benefits from the new approach in frail, elderly patients are to provide a safe and efficient treatment in a patient group that is considered not fit enough to undergo the standard treatment. Through a 3+3 model, the Maximum Tolerated Dose (MTD) will be assessed to be used in the following Phase II trials. The use of TG02 in patients after first relapse can be a new efficient treatment in a disease setting where a standard of care has not yet been established.

Risks

On the other hand, there are risks about these treatments, and especially during the COVID-19 crisis, that are increased:

The fact that included patients need to come for regular visits to the hospital increases their exposure risk to persons who are contagious for COVID-19. General rules like social

distancing and avoidance of persons with possible signs or confirmed diagnosis can be applied. But COVID-19 may also be contagious in persons who do not have symptoms. And age alone might be a very important risk factor for dying from COVID-19 infection.

The treatment regimens in all 3 arms of 1608 (Radiotherapy or chemotherapy with TG02 (arms A and B) and as a single agent (arm C)) decrease the patients' immune function temporarily via bone marrow suppression. This may lead to an increased risk of acquiring COVID-19 infection.

Deviations from the protocol treatment regimen, e.g. delays or interruptions that are COVID-19 related, can negatively influence the efficacy of the drugs and thus the benefits of the treatment for the patients.

Proposed measures for patients already enrolled during the COVID-19 crisis and recruitment

The study coordinators in collaboration with EORTC, propose the following guidelines as long as the current COVID-19 crisis is ongoing.

Please ensure that any protocol deviations resulting from COVID-19 crisis are reported to the EORTC study team ([contact]) without delay, so can be adequately reported to regulatory bodies if needed.

Please ensure that each deviation to the protocol instructions are adequately documented in the eCRFs as well as in the patient's medical records or in a Note to File (NTF) to be stored in your Study binder (ISF).

N.B. Always specify the reason of the deviations: "COVID-19".

1. Specific Guidelines during COVID-19 PandemicCOVID-19 vaccination:

As per the European Medicines Agency (EMA):

If physicians decide to administer SARS-CoV-2 vaccines in patients enrolled in the study, decisions should be individualized based on the risk of SARS-CoV-2 complications and potential benefit from the vaccine, general condition of the patient and the severity of COVID-19 outbreak in a given area or region and in accordance with the vaccine label. Furthermore, the country guidelines and/or institutional guidelines, must be followed.

The available SARS-CoV-2 vaccines, that are not live attenuated vaccines, are not contra-indicated in patients on immunotherapy.

Treatment schedule should not be altered because of the COVID-19 vaccination.

The administration of a SARS-CoV-2 vaccine including the name of the vaccine (e.g. Moderna, Pfizer BioNTech, AstraZeneca Oxford, ...) shall be added in the concomitant medication form in the eCRF and noted in the patient's Medical file. Any possible vaccine related AE should be captured in the AE forms in the eCRFs, specifying the potential relationship to the vaccine.

2. Guidelines for study assessments

2.1 With respect to study imaging procedures:

For the baseline study imaging procedures, the protocol requirements have to be fully met.

For on-study imaging procedures, it is preferred that the patient have imaging performed at the investigative site as directed in the protocol.

If difficulties are encountered to perform the imaging as directed in the protocol, there are several possibilities, in order of preference:

Have the imaging performed offsite/locally according to the protocol-specified timing. Guidance should be given by the site to the local imaging facility about conducting scans according to all applicable requirements (modality etc. as per 1608 Imaging Guidelines).

Have the imaging performed at the site but delayed to a significant extend (a window of 2 weeks instead of 1 week will be allowed) due to travel restriction/safety of the participant.

Have the imaging performed offsite but delayed (a window of 2 weeks instead of 1 week will be allowed) due to travel restriction/safety of the participant.

Skip the imaging only if impossible to perform due to travel restriction/safety.

Note: If a patient cannot go to site to receive the imaging results because of safety or isolation or travel risks, the results can be communicated by telephone, video visit.

2.2 With respect to study treatments:

In general, patients with a deadly cancer such as anaplastic astrocytoma or glioblastoma should receive the best possible treatment, also during the ongoing pandemic. Withholding or interrupting tumor-specific treatment should therefore be avoided whenever possible. For the ongoing EORTC-1608-BTG (STEAM) trial, the goal is therefore – taking in account guidance of local and national authorities - to treat patients as closely to the protocol guidelines as possible, without endangering their safety and keeping the risk / benefit ratio for the patient acceptable.

Patients on treatment will be treated as per protocol, in all arms. Protocol assessments should be performed as per protocol as much as possible, taking in account local and/or national guidance.

Assessments should be done at the investigative site if possible.

In the event it is not possible or not in the best interest of a patient to travel to the treating site because of COVID-19, the following options are proposed:

- If assessments are required prior to study treatment (TG 02/ TMZ) administration, as stated in the protocol and administration of study treatment cannot be postponed the following should be considered:

Arrange the exact date of the visit (and time) in the center and perform the assessments in advance

Provide standard laboratory assessments of the subject either by qualified staff of contracted laboratories or contractually secured healthcare providers whom employ appropriate safety measures and excludes patients whom are quarantined or living with or have been quarantined with a confirmed COVID-19 case

- Treatment related laboratory exams can be done in certified off-site facilities.

Visits that do not involve administration of study treatment, and that cannot be met because of the COVID-19 crisis can be replaced by a telephone consultation.

These deviations will not to be considered as protocol violations and must be documented clearly both in the eCRFs as well as in the patients' medical file on site as a COVID-19-related deviation (please specify every deviation in the eCRF with "COVID-19"). All other COVID-19-related deviations to the protocol will be documented equally. In case of doubt, the 1608 medical monitor can always be contacted to discuss ([contact] / [contact]). COVID-19-related deviations will not be considered protocol violations as long as they do not endanger the safety of the patient.

- With respect to **TG02 (in Arms A, B and C)**

Patients should be seen at the participating site at every planned visit if possible. If hospital visits are not possible because of travel restrictions or safety issues, the per protocol assessments may be performed offsite, see above, and patients may receive TG02 supply through courier from site to their home address under responsibility of the PI and the pharmacist. In this case, please always contact the EORTC study team. The process for shipping directly to subjects from sites must be fully documented and traceable.

Important note: Patient should be reminded to complete patient diaries.

Before the continuation of TG02, the investigator must provide his/her approval to the patient or the qualified person in charge of patient care, based on the assessments performed as per protocol.

- With respect to **Temozolomide (TMZ)**

TMZ will continue to be provided to the patient as per the sites local practice.

2.3 With respect to shipment of investigational medicinal products to subjects:

In case of home delivery, please inform patients about the following:

To insure the continuity of your treatment and therefore your vital interests, your name and address will be communicated by your investigator or the staff of your hospital to the organization responsible for the drug supply.

EORTC and/or your hospital will ensure that your name and address are processed in the secure way and are not used for any other purpose than for delivering your drugs to you

EORTC and/or your hospital will ensure that this additional information is not anymore stored by the drug suppliers once these exceptional measures are over and your treatment and/or follow-up are back to the normal

Important note: Investigators should be informing their patients about the fact that drug suppliers will be receiving their name and address for delivery and that they will not store this information beyond the crisis should be reminded to complete patient diaries.

2.4 With respect to patient physical visits:

Patient physical visits which are not crucial for the safety of the patient and that cannot be met because of the COVID-19 crisis can be replaced by a telephone consultation.

- With respect to patient reported data

Quality of Life (QoL) and G8 questionnaires can be collected through phone or a video conference. Voice scripts are available on the study web documentation for the QoL questionnaires.

If phone assessment cannot be arranged, the QoL and G8 questionnaires can be collected by providing the questionnaires to the patients. Patients should be instructed to complete the questionnaires within the intended timepoint (according to protocol). Patients should also complete the date on the form with the date they completed the questionnaire. Sites are requested to make their own guidelines to patients in their own language.

2.5 With respect to collection of biomaterial:

If the collection of a sample is part of the inclusion criteria (only arm A & B - FFPE tumor tissue block or 24 tumor tissue slides 5µm) and if impossible to collect the sample(s) due to travel restriction and/or safety concerns, the patient cannot be enrolled in the trial.

The collection of sample(s) can be skipped only if all following (2) criteria are met

- The HBM samples are not part of the inclusion criteria and
- The collection of the HBM samples is impossible to perform due to travel restrictions and/or safety concerns

If these 2 criteria are fulfilled, the sample collection can be skipped and a deviation must be entered, as this was not according to the protocol.

Please begin deviation text with "COVID-19" followed by the reason of the non-collection

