6.1 Before treatment start

6.1.1 Registration

6.1.1.1 Groups A and B

These assessments must be completed within 28 days prior to enrollment

- Histological diagnosis of glioblastoma or anaplastic astrocytoma
- Informed consent for phase 1b
- FFPE block or 25 unstained slides. The slides or the block MUST be sent to [REDACTED] [REDACTED] for MGMT analysis as soon as the patient has signed the consent form. Results are needed before enrollment onto the study for these two groups (for more information see sections 7.1.9, 13.1.2 and HBM guidelines provided as separate document).
- Evaluation of inclusion and exclusion criteria
- Medical history, including prior cancer

These assessments must be completed within 14 days of enrollment

- Complete physical examination, including any ongoing clinical symptoms. For female patients, menopausal status should be documented.
- Concomitant medications assessment
- Steroid dose. For corticosteroids, dose, frequency, dates of administration and route of administration must be recorded in the dedicated eCRF.
- Vital signs: blood pressure, pulse, temperature, weight, height
- Karnofsky Performance Status (KPS) (see Appendix E)
- Hematology: hemoglobin, hematocrit, total WBC count with differential (neutrophils and lymphocytes), and platelet count
- Biochemistry: sodium, potassium, chloride, BUN, creatinine, total protein, albumin, AST, ALT, total bilirubin, alkaline phosphatase, calcium, magnesium, LDH, glucose, creatinine kinase and phosphate
- Coagulation: PT, PTT and INR
- Complete neurological examination (NANO, see section 7.2.4)
- Quality of life assessment (modified EORTC QLQ C30/BN20) (see Chapter 10 and Appendix F)
- Geriatric evaluation (G8) (see Appendix G)
- 12-Lead ECG

This assessment must be scheduled within 14 days of first dose of TG02

- Brain gadolinium (Gd)-MRI. If a 72-h post-surgery MRI was done and falls within this time window, baseline MRI does not need to be repeated. See Section 7.2.5 and Appendix J for detailed MRI sequences. Additional information can be found in the study specific imaging guidelines.

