7.4.2 Assessments

G8 will be measured in all patients in groups A and B. G8 has to be completed by the clinician, the nurse or the trained coder. This screening tool includes 7 items of the Mini Nutritional Assessment and the age of the patient. The English version of G8 is included in Appendix G.

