8.2.3 Pre-planned sensitivity or exploratory analyses

As sensitivity analysis in group C, PFS and OS analyses will also be presented in the intent to treat population.

As exploratory analysis, in group A and B, baseline frailty scores will be correlated with safety, tolerability and efficacy.

In all groups, correlation of molecular markers including MYC, MCL-1, CDK9 and CDK5 proteins level (but not exhaustively) with response, success, PFS and OS will be explored.

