Appendix G: G8 geriatric screening tool (Version 1.0 - December 2010)

To be completed by: Clinician, nurse or trained coder.

Notes: This screening tool includes 7 items of the Mini Nutritional Assessment and the age of the patient.

Score: Total score by adding up coded answers.

G8 Screening tool			
	Items	Possible answers	Score
A	Has food intake declined over the past 3 months due to loss of appetite, digestive problems, chewing or swallowing difficulties?	0: severe reduction in food intake 1: moderate reduction in food intake 2: normal food intake
B	Weight loss during the last 3 months?	0: weight loss >3kg 1: does not know 2: weight loss between 1 and 3 kg 3: no weight loss
C	Mobility	0: bed or chair bound 1: able to get out of bed/chair but does not go out 2: goes out
E	Neuropsychological problems	0: severe dementia or depression 1: mild dementia or depression 2: no psychological problems
F	Body Mass Index (weight in kg/height in m ²)	0: BMI less than 19 1: BMI 19 to less than 21 2: BMI 21 to less than 23 3: BMI 23 or greater
H	Takes more than 3 medications per day	0: yes 1: no
P	In comparison with other people of the same age, how does the patient consider his/her health status?	0: not as good 0,5: does not know 1: as good 2: better
	Age	0: >85 1: 80-85 2: <80
	Total score (0-17)	

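### Appendix L's COVID-19 fallback lets patients complete the G8 themselves, against 7.4.2 and Appendix G, so some baseline frailty scores can rest on self-rated dementia/depression and self-derived BMI.

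*Combined protocol and SAP*

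**What the plan says.** Two places name the rater. Section 7.4.2 states that "G8 has to be completed by the clinician, the nurse or the trained coder", and the form in Appendix G carries the instruction "To be completed by: Clinician, nurse or trained coder".

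Appendix L, which applies only during the COVID-19 crisis, places the G8 under patient-reported data in its section 2.4. Its first option is remote contact: "Quality of Life (QoL) and G8 questionnaires can be collected through phone or a video conference". Its second option is the one at issue: "If phone assessment cannot be arranged, the QoL and G8 questionnaires can be collected by providing the questionnaires to the patients". The text that follows has patients fill in and date the forms, and leaves each site to write its own guidance for them. Scripts for telephone use are mentioned for one instrument only: "Voice scripts are available on the study web documentation for the QoL questionnaires".

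The G8 is taken once. Section 6.1.1.1 puts it within 14 days of enrollment, the summary tables for Groups A and B place it at registration, and section 7.4.3 says that it is not a follow-up tool. Relating frailty to safety, tolerability and outcome is a secondary objective for Groups A and B (2.1.2). Section 8.2.3 plans it as an exploratory analysis in which "baseline frailty scores will be correlated with safety, tolerability and efficacy", with no provision for how the form was completed.

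**The concern.** The G8 is built to be scored by a rater. Item E grades dementia or depression, item F needs BMI calculated from weight and height, and item P asks in the third person how the patient sees his or her own health. Appendix L handles it like the quality-of-life questionnaire, where the patient's own answer is the measurement, and reserves no item for staff.

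The patients are over 65, have a high-grade glioma and are considered unfit for combined treatment. Self-grading of dementia is doubtful in such a group. If some forms are staff-scored and others self-scored, the mode of completion becomes a source of error in the only frailty measure that the trial collects. No later G8 replaces a poor baseline form.

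**Working it through.** **1. Reproduce the form's range.** The item maxima in Appendix G are A 2, B 3, C 2, E 2, F 3, H 1, P 2 and age 2. All minima are 0.

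- Maximum: 2 + 3 + 2 + 2 + 3 + 1 + 2 + 2 = 17.
- Range: 0 to 17, which matches the form. (Section 7.4.1 gives 1 to 17. This is a separate slip that can be corrected at the same time.)

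**2. Which items self-completion puts in doubt.**

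- Item P is the patient's own view by design. Items A, B and C are questions that a patient can answer to staff by phone. None of these is the problem.
- Item E is a clinical rating, worth up to 2 points.
- Item F is a calculation from weight and height, worth up to 3 points.
- Item H is a yes/no question on taking more than three medicines a day. Staff can check it and age against records, so I do not count them as at risk.
- E + F = 2 + 3 = 5 points, and 5/17 = 29% of the scale.

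**3. How much E and F matter to a total.** The other six items sum to at most 17 − 5 = 12.

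- A score above 14, the level that 7.4.1 treats as low risk, therefore needs at least 3 points from E and F, because 12 + 2 = 14 is not above 14.
- The lowest other-item sum that can still pass is 9.5, because 9.5 + 5 = 14.5 while 9 + 5 = 14.
- So for a patient with 9.5 to 12 points on the other items, E and F alone decide the side of 14. This shows their weight in the score. It is not an error in the 8.2.3 analysis, which sets no cut-off.

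**4. What staff already hold at registration.** Section 6.1.1.1 requires, within 14 days of enrollment, a physical examination, "Vital signs: blood pressure, pulse, temperature, weight, height", a concomitant medication assessment and the NANO examination.

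- Item F can be derived from weight and height, and item H from the medication list. Age follows from the birth date or year.
- Item E cannot be derived in the same way. No listed assessment grades dementia or depression. The nearest NANO domain, Behavior, covers features such as apathy, disinhibition and confusion, which do not map onto item E. A clinician has to rate it.

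**5. How many patients.** Groups A and B have at most 24 + 12 = 36 evaluable patients. The number who used the fallback is not given, so the size of the error cannot be computed.

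**The case against.** The strongest reply is that this is a narrow, deliberate and temporary exception. It applies only during the crisis and only when phone assessment cannot be arranged. Staff should normally see the patient for the registration examination anyway, and Appendix L still requires the baseline imaging requirements to be fully met, so the route may seldom be needed. COVID-19 deviations must be labelled and documented, so self-completed forms may be traceable. The analysis is exploratory, and section 8.2.2 makes Groups A and B descriptive. All of this stands, and it keeps the point small. It does not remove the conflict over who completes the form, and labelling a form does not correct its score.

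A reader might infer more than the documents support:

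- **That the baseline scores do contain self-ratings.** Nothing shows that any G8 was self-completed.
- **That impaired patients drift upward and the frailty association is diluted.** Item E also covers depression, which a patient could over-rate as well as under-rate. The direction is unknown.
- **That item E would typically shift by 2 points.** That requires a true rating of severe dementia or depression, which is unlikely in patients who must be able to understand the study and give written consent. A one-point error is more plausible.
- **That patients are misclassified at 14.** Section 8.2.3 correlates scores and specifies no dichotomy.
- **That every item can be re-scored from existing data.** This holds for F, H and age, but not for E.

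**Conclusion.** The point holds in limited form. Section 7.4.2 and Appendix G require a staff rater, while Appendix L permits the patient to complete the form as a last resort during the pandemic. For patients who use that route, up to 5 of 17 points in the only frailty score can be self-rated or self-derived. Mixed modes then add error of unknown size and direction to one exploratory correlation in at most 36 evaluable patients. The MTD, the recommended dose and the Group C endpoint do not use the G8 and are unaffected.

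This rests on two readings: that handing over the form means the patient scores it, since Appendix L assigns no item to staff, and that 8.2.3 makes no allowance for mode because it mentions none. The change is worth making because it is cheap, not because harm has been shown.

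**What to change.** - In Appendix L 2.4, remove the G8 from the self-completion sentence. Keep phone or video administration by staff.
- State that the clinician, nurse or trained coder always scores the form. Items F, H and age come from the registration weight and height, medication list and birth year. Item E is rated by the clinician at the registration examination.
- Record the mode of completion for each G8.
- For any self-completed form already received, re-derive F, H and age from the registration data. Have the clinician rate item E from the medical record or, failing that, flag it. Repeat the 8.2.3 correlation without those forms as a sensitivity analysis.

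The cost is a short edit to Appendix L, one recorded field and one repeat of an exploratory analysis. Going forward, the inputs for F, H and age are already collected, and item E needs a rating at an examination that takes place anyway. The downside is that an occasional G8 may be incomplete if staff cannot reach the patient.
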